Researchers will have access to all patients scheduled for delivery at Mount Sinai Medical Center. About 1800 deliveries by cesarean section occur each year at Mount Sinai. Of these, approximately 800 are cesarean sections after failed labor. Assuming a primary outcome rate of 20% in the control arm, a sample size of 329 in each group would give 80% power to detect a 40% reduction in surgical site infection between the active group and control. We aim to recruit 400 patients per group (for a total of 800 patients) to account for patient drop out or non-compliance.

Description of Procedures Being Performed

This study intends to evaluate the effectiveness of a chlorhexidine gluconate (CHG) cloth and vaginal scrub in reducing SSI in patients undergoing cesarean section who have previously been laboring. Patients will be randomized to one of two groups: administration of a 2% CHG cloth and vaginal scrub (in addition to standard preoperative care) prior to cesarean delivery or standard preoperative care.

Description of the Source Records that Will Be Used to Collect Data about Subjects

All data will be extracted from electronic medical records (EMR) and phone calls made to subjects if they do not present for their postpartum visit.

Description of Data that Will Be Collected Including Long-Term Follow-Up

Data that will be collected from the EMR include maternal demographics (age, race, BMI, parity) as well as outcomes including surgical site infection and postpartum endometritis. In addition data will be collected regarding other outcomes including maternal complications or interventions, neonatal ICU admissions, maternal length of stay or readmissions. This data collection will start from time of enrollment to 6 weeks postpartum.

Where and When Consent Will Be Obtained

Consent will be obtained upon admission to the labor and delivery floor at Mount Sinai Hospital.

Waiting Period for Obtaining Consent

The patient can be approached and consented starting from admission to labor and delivery and can still be consented to participate in the study at a later time in labor if not already delivered by cesarean section.

Description of Health Information That Will Be Viewed, Recorded, or Generated

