Health information collected will include maternal age, parity, gestational age, medical problems, number of previous cesarean sections, indication for cesarean section, time from incision to delivery, type of anesthetic, type and use of prophylactic antibiotics and type of wound closure. Maternal outcomes including estimated blood loss (EBL) will be reviewed. Charts will be reviewed through the 6 week postpartum visit in order to determine how well the skin at the incision site is healing. If patients do not visit Mount Sinai Medical Center for their 2 week wound check, they will be called and asked the following questions: Were you treated for wound infection? Did you experience wound separation or any other wound complications?

Description of Non-Health Information That Will Be Viewed or Recorded

Data collected will include demographic variables such as age, parity, body mass index (BMI) and race.

How PHI Will Be Protected from Improper Use or Disclosure

No specimens will be sent out or received in this trial.

All data is de-identified; patients are followed by subject number. Identifiable patient information (consent forms & consent documentation) are kept separately from any data collected. All consent documentation is stored in a locked cabinet at [REDACTED]. Identifiable enrollment statistics are kept in a password-protected computer (Excel) spreadsheet that is only accessible by members of the research team on a departmental J Drive.

When and How PHI Will Be Destroyed

The key code and data points will be destroyed 7 years after data analysis is complete.

Description of PHI that Will Be Shared

PHI that will be shared will include maternal demographics and maternal outcomes as previously described. Maternal demographics and information collected will include age, parity, BMI, race, gestational age, and number of previous cesarean sections. Additional information will be recorded and shared including time from incision to delivery, type of anesthetic, antibiotic use, type of wound closure, and EBL. Charts will be reviewed through the 6 week postpartum visit in order to determine how well the skin at the incision site is healing.

Justification for Sharing PHI

The PHI will be shared for means of data analysis by members of the research team and statisticians.

With Whom Directly PHI Will Be Shared

The PHI will be shared with members of the research team

Location Where Data Will Be Stored

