All research data will be stored in a password-protected database maintained on a secure network drive on the hospital server.

Duration Data Will Be Stored

The key code and data points will be destroyed 7 years after analysis is complete.

Steps That Will Be Taken to Secure the Data During Storage, Use, and Transmission

To minimize risk of loss of confidentiality, study subjects will be assigned a unique identification code. The unique ID code will be linked to the subject's medical record number. The linking key code will be encrypted and stored separately on a secure excel spreadsheet accessible only by the PI and research staff. All research data will be stored in a password-protected database maintained on a secure network drive on the hospital server.

Steps That Will Be Taken to Secure the Data During Storage, Use, and Transmission

To minimize risk of loss of confidentiality, study subjects will be assigned a unique identification code. The unique ID code will be linked to the subject's medical record number. The linking key code will be encrypted and stored separately on a secure excel spreadsheet accessible only by the PI and research staff. All research data will be stored in a password-protected database maintained on a secure network drive on the hospital server.

Data Analysis Plan Including Any Statistical Procedures

Data will be analyzed on an intention to treat basis. Statistical analysis will be performed by SAS using X 2 test or Fisher exact test (categorical variables) and student t test or Mann-Whitney U test (continuous variables). Statistical significance will be set at $p<0.05$.

Study Fund Account (or alternate departmental / fund account, if study is not yet established)
[REDACTED]

Generic Name

4% chlorhexidine gluconate

Brand Name

BD E-Z Scrub 107 Surgical Scrub Brush/Sponge 4% Chlorhexidine-Gluconate

IND Number

[REDACTED]

Name of IND Holder

[name]

Drug / Biologic Description (Manufacturer/Generic Name/Form/Strength)

Drug: BD E-Z Scrub 107 Surgical Scrub Brush/Sponge 4% Chlorhexidine-Gluconate

Biologic Description: Antiseptic

Manufacturer: Becton, Dickinson and Company

Generic Name: 4% chlorhexidine gluconate

Form: Scrub Brush/Sponge

Strength: 4% chlorhexidine gluconate w/v

Effective Date: 3/11/2022

End Date: 3/10/2023

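### The unadjusted primary test is valid, but prespecified adjustment for a few baseline factors already on the data list would add a modest amount of power

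*Combined protocol and SAP*

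**What the plan says.** The section headed Data Analysis Plan Including Any Statistical Procedures is three sentences long. It sets an intention-to-treat basis and a 0.05 significance level, and it names the tests. For categorical outcomes the wording is "Statistical analysis will be performed by SAS using X 2 test or Fisher exact test (categorical variables"). The primary outcome, under Primary and Secondary Study Endpoints, is SSI and postpartum endometritis. I read this as a binary composite, so this is the test that applies to it. No adjusted model, stratified test or stratification factor for randomisation appears anywhere.

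Two other sections list baseline factors. Under Description of Data that Will Be Collected: "Data that will be collected from the EMR include maternal demographics (age, race, BMI, parity"). Under Description of Health Information, maternal age, parity and gestational age come first, followed by "medical problems, number of previous cesarean sections, indication for cesarean section". The same section also lists intra-operative items.

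The sample size statement reads: "Assuming a primary outcome rate of 20% in the control arm, a sample size of 329 in each group would give 80% power". The effect it refers to is a relative fall of 40% in the active arm. The target is then raised: "We aim to recruit 400 patients per group (for a total of 800 patients) to account for patient drop out or non-compliance".

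**The concern.** A crude comparison of two proportions treats all variation in infection risk between women as noise. If BMI, parity, previous cesareans or gestational age explain part of that variation, a model that includes them estimates the treatment effect more precisely from the same women. Without stratified randomisation or an adjusted analysis, nothing in the plan accounts for a chance imbalance in these factors.

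Two things are at stake. One is a few points of power in a design that sits at 80% when 329 per group are analysed; the other 71 per group are set aside for dropout and non-compliance. The other is prespecification. If an adjusted analysis is wanted later, its covariates would be chosen with the results in view unless they are named now.

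**Working it through.** **Inputs.** From the documents: control risk 20%; a 40% relative reduction, so 0.20 × 0.6 = 12% with treatment; 329 per group needed and 400 recruited; significance level 0.05. Assumed: two-sided testing, since sidedness is not stated, and the prognostic strength of the covariates, which the documents do not give.

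**1. The plan's own figure.** With pooled variance under the null and p̄ = 0.16:

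n = [1.96 √(2 × 0.16 × 0.84) + 0.8416 √(0.20 × 0.80 + 0.12 × 0.88)]² / 0.08²

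= [1.96 × 0.5185 + 0.8416 × 0.5154]² / 0.0064 ≈ 2.102 / 0.0064 ≈ 328.5, so 329 per group.

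Power at 329 is 80.1%, and at 400 it is 87.1%. The planned test and the sample size agree.

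**2. Adjustment as a variance reduction.** If the covariates explain a share R² of outcome variance, n women carry the information of n/(1 − R²). The number giving the precision of 329 unadjusted is 329 × (1 − R²), rounded up.

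| Assumed R² | Power at 329 | Equivalent n per group | Power at 400 |
|---|---|---|---|
| 0 | 80.1% | 329 | 87.1% |
| 0.01 | 80.5% | 326 | 87.5% |
| 0.02 | 80.9% | 323 | 87.8% |
| 0.05 | 82.0% | 313 | 88.8% |
| 0.10 | 84.0% | 297 | 90.3% |
| 0.15 | 86.0% | 280 | 91.9% |

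For R² between 0.01 and 0.10, the gain at 329 is 0.4 to about 4 points, equivalent to 3 to 32 women per group.

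**3. Simulation of the proposed analysis.** Outcomes were drawn from a logistic model with a normally distributed linear predictor. Intercepts were set so that the marginal risks were 20% and 12%. The unadjusted chi-square was compared with a standardised risk difference from a four-covariate logistic model, at 329 per group:

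| Linear-predictor SD | AUC (approx.) | Unadjusted to adjusted, 4,000 trials | Unadjusted to adjusted, separate run of 2,000 trials |
|---|---|---|---|
| 0 | 0.50 | 80.6% to 80.7% | no meaningful change |
| 0.4 | – | – | gain of about 0.5 point |
| 0.6 | 0.66 | 79.8% to 81.7% | 80.2% to 81.7% |
| 0.8 | 0.71 | 79.8% to 83.1% | – |
| 1.0 | 0.75 | 80.5% to 84.8% | 80.9% to 85.9% |

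Monte Carlo error in the 4,000-trial column is about 0.6 point per estimate. A six-covariate logistic Wald test gave a similar picture: 79.9% to 80.0% at AUC 0.58, and 81.4% to 85.4% at AUC 0.75.

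**4. Lower event rates.** The background section puts infectious morbidity at 5–10% of cesareans. With the same 40% reduction, expected events at 329 per group are:

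- 20% control risk: 329 × (0.20 + 0.12) ≈ 105
- 10% control risk: 329 × (0.10 + 0.06) ≈ 53
- 5% control risk: 329 × (0.05 + 0.03) ≈ 26

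At 10% versus 6% and 329 per group, power went from 46.0% to 46.6% with no signal. At SD 0.6, 0.8 and 1.0 it went from 47.5% to 49.5%, from 47.4% to 49.9%, and from 47.5% to 51.4%. At 400 per group and SD 0.6 it went from 55.0% to 56.4%. Allowing for simulation error, this is a gain of about 0.5 to 3 points; the largest single run gave 3.9.

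**5. Type I error.** With four covariates and null risks of 20%, 10% and 5%, the adjusted test rejected in 4.6% to 5.8% of trials and the crude test in 4.3% to 5.7%. The 2,000-trial run at 10% and 5% gave 4.2% to 6.1% for the adjusted test. Its Monte Carlo error is √(0.05 × 0.95 / 2,000) ≈ 0.5 point. The sparsest of these settings has about 658 × 0.05 ≈ 33 events in total.

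**The case against.** The strongest reply is that nothing here is wrong. Randomisation makes the chi-square valid without covariates, the test matches the basis of the 329, and the plan reaches its own power target unadjusted. All of that stands. A reader might infer that the crude test is biased by chance imbalance or leaves the trial short of its stated power; the documents support neither.

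The gain also rests on prognostic strength that has to be assumed. This stands too. With weak covariates it is half a point or less, and parity and previous cesareans overlap, so together they may add less than four independent covariates would.

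The gain shrinks when events are few. At 400 per group and SD 0.6, an adjusted logistic test gave 55.3% against 55.0% crude at 10% versus 6%, and 29.1% against 29.7% at 5% versus 3%. The standardised risk difference did slightly better (56.4% and 31.3%). Part of that edge may come from its variance estimate and not from covariate information. Adjustment would not rescue a trial whose event rate is far below 20%. Even so, with four covariates type I error stayed close to nominal, so sparse events argue for a short list and a fallback, not against adjusting.

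Three further inferences go too far. It is tempting to say that precision is given up at no cost, but a rule for missing covariates and a fallback are needed. It is tempting to assume complete covariates for every woman, but the protocol lists the items without saying they will be complete. And because participants are unblinded, adjustment might seem to protect against that; it does nothing about biased ascertainment of outcomes.

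**Conclusion.** The point holds as a missed efficiency gain, not as an error. The only planned test of the primary outcome is crude, and usable baseline factors are already listed for collection. At 329 per group and 20% versus 12%, prespecified adjustment is worth about 0 points of power with no or weak signal, rising to about 4 to 5 points at a linear-predictor SD of 1.0 (AUC about 0.75). At 10% versus 6% it is worth about 0.5 to 3 points. These figures assume two-sided testing, a 40% reduction, complete covariates, and prognostic strengths chosen to span a range because the documents give none. The change is worth making because it is cheap and settles the covariates in advance. The trial's validity does not depend on it.

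**What to change.** Add one paragraph to the analysis plan before any outcome is analysed by arm.

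- **Primary analysis:** logistic regression of the composite outcome on arm, BMI, parity, number of previous cesareans and gestational age, with continuous terms kept continuous.
- **Primary statistic:** the standardised (marginal) risk difference, with its p-value and 95% CI from a robust standard error. Report the standardised risk ratio beside it. State that this p-value is the primary one.
- **Supporting analysis and fallback:** the chi-square or Fisher test, used as primary if the model does not converge or if events are very few. Fix the threshold for very few in advance and apply it to the event count pooled over arms.
- **Missing covariates:** a simple rule, for example single imputation done without reference to arm or outcome.
- **Exclusions:** no adjustment for anything measured after randomisation, such as incision-to-delivery time, wound closure or estimated blood loss. Indication for cesarean should also stay out, since women are approached at admission or during labor and it may arise after randomisation.

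The recruitment target need not change. The cost is the paragraph, a few lines of SAS, and the handling of missing values. If the covariates prove uninformative, no meaningful power is lost.
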